The 4-week rat and dog toxicology packages support the current clinical trial starting with a combination of [REDACTED] twice a day and [REDACTED] twice a day in cohort 1, followed by [REDACTED] twice a day and [REDACTED] twice a day in cohort 2. The pivotal toxicity studies performed in rats and dogs have shown that dog is the most sensitive species to STP1 treatment: the NOAEL was 3 mg/kg/day in male dogs which represents a 5-fold safety margin based on allometric scaling.

[REDACTED] has immunomodulatory and anti-inflammatory properties and, as such, should not be taken while an acute infection is ongoing. Therefore, patients with active infection, including (but not limited to) bacterial, fungal or viral infection, will not be included in the trial. Rare cases of thrombocytopenia have been reported with the use of [REDACTED] even though not expected at the dose levels used in this study and the short treatment duration, platelet count will be monitored throughout the study and patients with history of thrombocytopenia within the past year will not be included in the study. The use of other medication that could worsen possible thrombocytopenia will be used with precaution. [REDACTED] is predominantly cleared by CYP3A4 metabolism with to a lesser extent other CYP450 pathways (see Section 1.3.2). In order to avoid interference with the PK of STP1, moderate or strong CYP3A4 inhibitors (e.g., ketoconazole) are excluded. As a potent loop diuretic, [REDACTED] may trigger hypokalemia and hypotension. Changes in electrolyte levels and blood pressure (including orthostatic blood pressure [BP]) will be monitored at each post-dose study visit and other loop diuretics will be prohibited. PK drug-drug interactions between [REDACTED] are not expected since both compounds are metabolized by different pathways. Both drugs are inhibitor of BCRP transporter at subclinically relevant levels, but the effect of drug combination on BCRP is unknown and drugs that are substrate of BCRP should be used with caution during this clinical trial. It is

possible that because [REDACTED] is a diuretic, an effect on the renal clearance of [REDACTED] may be observed, leading to a reduction in [REDACTED] plasma level. Urinary drug levels of [REDACTED] will be assessed in this study to evaluate potential effects of [REDACTED] clearance.

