5.0 Analysis of Pharmacokinetics

5.1 Description of Pharmacokinetic Variables

PK sampling will be collected from all patients for measurement of plasma and urine concentrations of ibudilast and bumetanide.

Blood samples will be drawn on Days 1, 7, 14/15 and, optionally, between Days 16 to 18, and urine samples will be collected on Days 1 and 14 to determine concentrations of ibudilast and bumetanide. Non-compartmental analysis (NCA) will be utilized to analyze data from the sampling schema. See Table 1 for the PK sample schedule.

Table 1. PK Sampling Schedule

PK Schedule ^c		
Time	Plasma ^a	Urine ^b
Day 1	0.25, 0.5, 1, 2, 4, and 6h post-AM dose	0 to 6h post-AM dose
Day 7	Pre-AM dose	
Day 14 (only AM dose) and 15	Pre-AM dose and 0.25, 0.5, 1, 2, 4, 6, 8, 10, 12 and 24h post-AM dose	0 to 4h, 4 to 8h, and 8-12h post-AM dose
Between Days 16 to 18 ^d	48, 72, and 96 h post-AM dose of Day 14	

^a Both ibudilast and bumetanide will be analyzed from the same blood draw for each specified sampling time point.
^b Urine creatinine from the urine collection will be paired with a serum creatinine measurement to evaluate completeness of collection.
^c All of these timepoints have a 5-minute window.
^d Optional

The following PK plasma parameters will be estimated for each patient(as far as possible):

PK Parameter	Definition
$C_{max, Day 1}$	Maximum plasma concentration on Day 1
$C_{max,ss}$	Maximum plasma concentration at steady state
C_{Last}	Last measured plasma concentration following the last administration
C_{trough}	Minimum observed plasma concentration prior to drug administration
T_{max}	Time of maximum observed plasma concentration; if it occurs at more than one time point, T_{max} is defined as the first time point with this value
$t_{1/2}$	Terminal elimination half-life, calculated as $\ln(2)/\lambda_z$
AUC_{0-last}	Cumulative area under the plasma concentration time curve calculated from 0 to the last measured plasma concentration following the last administration using the linear trapezoidal method
$AUC_{0-tau (6h), Day 1}$	Area under the plasma concentration time curve to the end of the dosing period following the first administration
$AUC_{0-tau (6h), SS}$	Area under the plasma concentration time curve to the end of the dosing period (6h) following the last administration
$AUC_{0-12h, SS}$	Area under the plasma concentration time curve to 12 hours post dose following the last administration

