$AUC_{0-\infty}$	Area under the plasma concentration time curve extrapolated to infinity, calculated as $AUC_{0-last} + C_{Last}/\lambda_z$
V_z/F	Apparent volume of distribution
Cl/F	Apparent total body clearance
Accumulation Ratio	Ratio of accumulation of a drug, calculated by the following equation: $AR_{AUC} = AUC_{0-tau (6h), SS} / AUC_{0-tau (6h), Day 1}$ $AR_{Cmax} = C_{max,ss} / C_{max, Day 1}$

As the PK time schedules were different prior to the implementation of Version 4.0 (Amendment 3) of the clinical study protocol, the PK schedule of the first 4 patients is as follows:

Day 1

- Blood sampling at pre-AM dose and 0.25, 0.5, 1, 2, 4, 6 h post-AM dose
- Urine sampling at 0 to 6 h post-AM dose

Day 7

- Blood sampling at pre-AM dose

Day 14

- Blood sampling at pre-AM dose and 0.25, 0.5, 1, 2, 4, 6, 8, 10, 24 and 30 h post-AM dose
- Urine sampling 0 to 6 h and 24 to 30 h post-AM dose

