5.2 Analysis of Pharmacokinetic Variables

Plasma and urine sample concentrations of ibudilast and bumetanide will be summarized by treatment, visit and time point using descriptive statistics.

Individual plasma concentrations of ibudilast and bumetanide will be depicted for each patient by treatment group using linear scale. Individual and mean plasma concentration- time profiles will be plotted in linear and semi-logarithmic scales.

PK parameter values will be summarized by treatment group using descriptive statistics (n, mean, SD, CV%, geometric mean, and 90% confidence interval). Plasma PK parameters such as $AUC_{0-\tau}$, AUC_{last} , C_{max} , T_{max} , C_{trough} , apparent oral clearance, the elimination half-life, apparent volume of distribution and accumulation ratios will be calculated following single dose administration (as far as possible) and at steady state for both parent drugs.

Urine parameters include the following:

- Excretion rate by timepoint:
 - Day 1, 0-6h
 - Day 14, 0-4h
 - Day 14, 4-8h
 - Day 14, 8-12h
- Cumulative excretion, based on Day 14 sampling over 0-12h
- Renal clearance, based on Day 14 sampling over 0-12h

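### SAP 5.2 yields no Day 14 excretion rate, cumulative excretion or renal clearance for the first 4 patients, whose urine was collected over different intervals

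*SAP*

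**What the plan says.** SAP 5.1 gives two urine schedules.

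- **Current schedule (SAP Table 1).** Day 14 urine is collected "0 to 4h, 4 to 8h, and 8-12h post-AM dose", and Day 14/15 plasma includes a 12 h sample.
- **Schedule before protocol Version 4.0.** The SAP states that "the PK schedule of the first 4 patients is as follows". For these patients Day 1 is "Urine sampling at 0 to 6 h post-AM dose" and Day 14 is "Urine sampling 0 to 6 h and 24 to 30 h post-AM dose". Their Day 14 plasma times run from pre-dose to 10 h, then 24 h and 30 h.

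SAP 5.2 lists the urine parameters: excretion rate for Day 1 0-6 h and for Day 14 0-4, 4-8 and 8-12 h; "Cumulative excretion, based on Day 14 sampling over 0-12h"; and "Renal clearance, based on Day 14 sampling over 0-12h". The shells for Tables 36 and 37 carry the same intervals and no others. SAP 5.2 also says: "Plasma and urine sample concentrations of ibudilast and bumetanide will be summarized by treatment, visit and time point using descriptive statistics".

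Protocol 1.5.2 gives the reason for the urine work. The diuretic may change the renal clearance of the other drug and lower its plasma level, so urinary drug levels "will be assessed in this study to evaluate potential effects" on clearance. Protocol 3.2.3 likewise names the diuretic's possible impact on the other drug's pharmacokinetics and excretion.

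**The concern.** The SAP recognises that the early patients were sampled differently, but it defines the Day 14 urine parameters only on the later intervals and gives no rule for the earlier ones. A programmer who follows it leaves every Day 14 cell of Tables 36 and 37 empty for these 4 patients. At stake is about half of the Cohort 1 active group for Day 14 renal clearance, which among the listed parameters bears most directly on the question the urine was collected to explore. A matching 0-6 h plasma area is already a defined parameter, so a clearance could be derived without any new sample.

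**Working it through.** **The plan's own figures.** The documents give no figure for the number of patients with a renal clearance. The related figures reproduce: 16/(1 - 0.20) = 20 enrolled, and 8 x 3/4 = 6 active with 2 placebo in Cohort 1.

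**Step 1: match the Day 14 intervals.**

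| SAP 5.2 Day 14 parameter | Interval needed | Available from the first 4 patients |
|---|---|---|
| Excretion rate | 0-4 h | No: one collection over 0-6 h, which cannot be split at 4 h |
| Excretion rate | 4-8 h | No |
| Excretion rate | 8-12 h | No |
| Cumulative excretion | 0-12 h | No: only 0-6 h of the 12 h is covered |
| Renal clearance | 0-12 h | No: urine as above, and no plasma sample between 10 h and 24 h |

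So 0 of these 4 patients have any listed Day 14 urine parameter.

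**Step 2: how many are on active drug.** Cohort 2 opens only after the 8 Cohort 1 patients finish and the DSMB reviews them, so the first 4 belong to Cohort 1: 4/8 = 50%. Only active patients inform clearance. If the order is treated as unblocked, the chance that k of the first 4 are active is C(6,k) x C(2,4-k)/C(8,4):

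- k = 2: 15 x 1/70 = 0.21
- k = 3: 20 x 2/70 = 0.57
- k = 4: 15 x 1/70 = 0.21

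The expected number is 4 x 6/8 = 3, and it would be exactly 3 with blocks of 4. The Protocol states permuted blocks but no block size. The loss is therefore 3 of 6 active patients, range 2 to 4 (33% to 67%).

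**Step 3: what this does to the planned summary.** SAP 5.2 plans 90% confidence intervals for PK parameters. The half-width, in units of the parameter's own between-patient SD, is t(0.95, n-1)/sqrt(n):

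- n = 2: 4.46 SD
- n = 3: 1.69 SD
- n = 4: 1.18 SD
- n = 6: 0.82 SD

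Cohort 1 Day 14 CLr over 0-12 h would rest on about n = 3 (range 2 to 4).

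**Step 4: what can be derived.** CLr = Ae(0-t)/AUC(0-t), where Ae is urine concentration times volume. Volumes are in Data Listing 14 and concentrations in Data Listing 16.

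- *Day 1.* Both schedules have 0-6 h urine and plasma to 6 h, and AUC0-tau(6h),Day 1 is defined. Ae(0-6 h)/AUC0-tau(6h),Day 1 is available for all 6 active patients in Cohort 1, on one interval.
- *Day 14, first 4 patients.* They have 0-6 h urine and plasma from pre-dose to 6 h, and AUC0-tau(6h),SS is defined. Ae(0-6 h)/AUC0-tau(6h),SS is available.
- *Day 14, later patients.* Their collections break at 4 h and 8 h, so a 0-6 h amount cannot be rebuilt.

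**Step 5: are 0-6 h and 0-12 h clearance the same quantity?** Protocol 1.4.1 gives a half-life of 1 to 1.5 h for the diuretic and about 19 h for the other drug. With simple exponential elimination, the fraction gone by time t is 1 - 2^(-t/half-life). At 6 h this is 1 - 2^(-6/1.5) = 0.94 for the diuretic, even at the longer half-life, against 1 - 2^(-6/19) = 0.20 for the other drug. A diuretic effect on clearance would thus weigh more in 0-6 h than in 0-12 h, so equality cannot be taken for granted.

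**The case against.** The strongest case on the other side has four parts.

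- **Most of the evidence survives.** The Day 1 0-6 h excretion rate is listed and was collected in everyone. Day 14 urine concentrations are summarised in Table 33 and listed in Data Listing 16. The 0-6 h plasma areas on Day 1 and at steady state are available for all active patients. The Protocol frames the interaction through plasma level as well as clearance. This stands. A reader might infer that Cohort 1 loses half its evidence on the interaction, or that the samples are thrown away; the documents support neither.
- **The SAP leaves room.** Its urine list is introduced as inclusive, and SAP 2.1 says data from all time points will be summarised as appropriate under the later sections. But Section 5 does not say how, and the table shells contain only the current intervals.
- **No Protocol endpoint is touched.** The Protocol specifies urine levels or concentrations; renal clearance is a SAP addition. This is correct and keeps the point minor.
- **One uniform interval is defensible.** A reader might infer that using 0-6 h data would give six comparable Day 14 clearances. It would not: about 3 would be on 0-6 h and about 3 on 0-12 h. This argues for separate display, not for leaving the values out.

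Two further limits also stand. Every active patient takes both drugs, with the diuretic dose fixed across cohorts, so there is no internal contrast. Protocol 1.4.1 also reports negligible unchanged parent drug in urine for ibudilast.

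**Conclusion.** The concern holds in a confined form. As written, the SAP produces no Day 14 excretion rate, cumulative excretion or renal clearance for the first 4 patients: 4 of 8 in Cohort 1, about 3 of 6 active, range 2 to 4. This is a stated definition that these patients' data cannot meet, not merely missing detail. The loss does not extend to Day 1 excretion, urine concentrations or 0-6 h plasma parameters, and no gain in precision should be claimed for a pooled Day 14 clearance.

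The count assumes that the first 4 patients are all in Cohort 1, that the block size is unknown, and that there is no dropout or missed collection. The point is minor: the study is descriptive, and renal clearance could say little about the interaction even with complete data. It is worth fixing because the data are already in hand.

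**What to change.** Amend SAP 5.2 and the shells for Tables 36 and 37 as follows.

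1. Add Day 1 CLr = Ae(0-6 h)/AUC0-tau(6h),Day 1 for all active patients. This is the one urine interval common to both schedules, so no pooling of unlike intervals is needed.
2. For the first 4 patients, add the Day 14 0-6 h excretion rate and CLr = Ae(0-6 h)/AUC0-tau(6h),SS. Label both by interval and show them separately from the 0-12 h values. Mark any pooled Day 14 summary as assuming similar clearance over the two intervals.
3. State that Day 14 cumulative excretion and CLr over 0-12 h are not derived for these 4 patients, and give the n behind each row.

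The cost is a short SAP revision and a few extra table rows. No new samples are needed. The tables become slightly longer, and inference on the interaction stays limited for the reasons given above.

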5.2 Analysis of Pharmacokinetic Variables

Plasma and urine sample concentrations of ibudilast and bumetanide will be summarized by treatment, visit and time point using descriptive statistics.

Individual plasma concentrations of ibudilast and bumetanide will be depicted for each patient by treatment group using linear scale. Individual and mean plasma concentration- time profiles will be plotted in linear and semi-logarithmic scales.

PK parameter values will be summarized by treatment group using descriptive statistics (n, mean, SD, CV%, geometric mean, and 90% confidence interval). Plasma PK parameters such as $AUC_{0-\tau}$, AUC_{last} , C_{max} , T_{max} , C_{trough} , apparent oral clearance, the elimination half-life, apparent volume of distribution and accumulation ratios will be calculated following single dose administration (as far as possible) and at steady state for both parent drugs.

Urine parameters include the following:

- Excretion rate by timepoint:
 - Day 1, 0-6h
 - Day 14, 0-4h
 - Day 14, 4-8h
 - Day 14, 8-12h
- Cumulative excretion, based on Day 14 sampling over 0-12h
- Renal clearance, based on Day 14 sampling over 0-12h

6.0 Exploratory Analyses

6.1 Description of Exploratory Variables

Exploratory variables for this study include:

- [REDACTED] and KiTAP subtask score
- OACIS-C
- ABC-C subscale scores
- SRS-2 subscale scores
- CSHQ total score
- Lactate and Pyruvate Blood Levels
- Change from baseline in CGI-S, as reflected by CGI-I
- Eye tracking
- EEG

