	
maximum plasma concentration (T_{max}) and accumulation ratio, apparent plasma terminal elimination half-life ($t_{1/2}$), apparent oral clearance and apparent volume of distribution (Vz/F).
 
• Urine level of [REDACTED] will be assessed on Days 1 and 14/15. 
Exploratory Endpoints - Pharmacodynamics:
 
• Change from baseline in subtasks from [REDACTED] and Cognition Battery and KiTAP test battery.• Global clinical change in the context of autism as measured by the change in the OACIS scale.• Change from baseline in ABC-C subscores.• Change from baseline in the SRS2-subscores.• Change from baseline in the CSHQ scores.• Change from baseline in the CGI-S scale, reflected by the CGI-I scale.• Change from baseline in electrophysiology parameters as measured by EEG at resting state and during habituation and chirp tasks.• Change from baseline in eye gaze to eye regions during viewing of static faces and change in eye gaze to social scene viewing during viewing of dynamic video.• Change from baseline in Lactate/Pyruvate ratio (L:P)

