Blinding	
The study will be blinded for patients/caregivers, study personnel with direct interaction with the subjects and vendors, using placebo capsules and tablets that match the active drugs in appearance, labelling and packaging. The total number of capsules making up each dose will be identical for both STP1 dose levels and placebo.
																		

	
Study personnel responsible for receiving the randomization lists and dispensing the assigned treatment will be unblinded. An independent DSMB will be appointed. The DSMB will be blinded to treatment for safety/tolerability assessments (primary outcome) and will advise on the start of 2nd dose level.

Statistical Methods	
For this Phase 1b study, descriptive statistics will be provided for all endpoints by treatment group. For continuous endpoints, summary statistics i.e., n (number of individuals included in the analysis), mean, SD, median, minimum, maximum, Quartile 1, and Quartile 3 will be provided. For categorical endpoints, the number and frequency in each category will be provided.
 
All subjects who have received at least one dose of the combination, whether prematurely withdrawn from the study or not, will be included in the safety analysis.
 
SAFETY and TOLERABILITY
 
The number of patients who report the following events will be summarized for all treated patients:
 
• AE and treatment-related AE.• AE and treatment-related AE that led to study treatment discontinuation.• SAE and treatment related SA.• SAE and treatment related SAE that led to study treatment discontinuation.• AESIs. 
Safety and tolerability are also measured by incidence and severity of AEs, physical examinations, ECG, vital signs, specific laboratory abnormalities and change from baseline in the CSHQ scores in all treated patients.
 
As this study will provide descriptive statistics, there will not be any correction for multiple primary endpoints.
 
PHARMACOKINETICS
 
The PK analysis set will include subjects with at least one sample collected and analyzed for plasma drug concentration. Concentration of each drug in plasma and urine will be listed and summarized by visit and nominal time. The NCA using the sampling mode of PK data and standard descriptive statistics for PK parameters will be calculated using Phoenix WinNonlin software (Certara).

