The Children Sleep Habits Questionnaire (CSHQ) is a retrospective, 45-item parent questionnaire that has been used in a number of studies to examine sleep behavior in young children. The CSHQ includes items relating to a number of key sleep domains that encompass the major presenting clinical sleep complaints in this age group: bedtime behavior and sleep onset; sleep duration; anxiety around sleep; behavior occurring during sleep and night wakings; sleep-disordered breathing; parasomnias; and morning waking/daytime sleepiness. Parents are asked to recall sleep behaviors occurring over a “typical” recent week. Items are rated on a three-point scale: “usually” if the sleep behavior occurred five to seven times/week; “sometimes” for two to four times/week; and “rarely” for zero to one time/week. Some items were reversed in order to consistently make a higher score indicative of more disturbed sleep [Owens et al, 2000]. The abbreviated version of this questionnaire includes 22 items assessing sleep habits and possible difficulties with sleep [Owens et al, 2000]. Unless noted, “always” refers to something occurring every night, “usually” if it occurs 5 or 6 times a week, “sometimes” if it occurs 2 to 4 times a week, “rarely” if it occurs once a week and “never” if it occurs less than once a week. Since the questionnaire is designed for children, the questionnaire will be answered by the parent/caregiver whenever possible. It should take approximately 5 to 10 minutes to be completed.

- Clinical Assessment of Suicidality

The assessment of suicidality will be collected for all patients at all visits using the Columbia Suicide Severity Rating Scale (C-SSRS) or the Columbia Classification Algorithm for Suicide Assessment (C-CASA).

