6.2 Analysis of Exploratory Variables

[REDACTED] and KiTAP

Summary statistics (n, mean, median, SD, minimum, and maximum) will be computed on the raw and change from baseline values for each subtask variable by visit, treatment and overall. The Day 1 time point will serve as baseline.

[REDACTED]

OACIS-C

Summary statistics (n, mean, median, SD, minimum, and maximum) will be computed on the raw score for each question will be summarized by treatment and overall. Frequency counts and proportions will also be summarized for each response in the assessment by treatment and for each group of responses (very much improved or much improved; minimally improved, no change or minimally worse; and much worse or very much worse).

ABC-C

Summary statistics (n, mean, median, SD, minimum, and maximum) will be computed on the raw and change from baseline scores for each subscale by visit, treatment and overall. The Screening time point will serve as baseline.

SRS-2

Summary statistics (n, mean, median, SD, minimum, and maximum) will be computed on the raw and change from baseline scores for each subscale by visit, treatment and overall. The Screening time point will serve as baseline.

CSHQ

The number and proportions will be summarized for each value in the assessment by visit, question, treatment and overall. The Day 1 time point will serve as baseline.

Lactate and Pyruvate Blood Levels

Summary statistics (n, mean, median, SD, minimum, and maximum) will be computed on the raw and change from baseline values of lactate, pyruvate and lactate-pyruvate ratio (L:P ratio) by treatment and overall. The Screening time point will serve as baseline.

Spaghetti plots of the raw values for L:P ratio will be displayed by patient, time point and treatment.

CGI-S and CGI-I

[figure not shown]
Frequency counts and proportions for each response to the CGI-S and CGI-I assessments will be summarized by treatment and visit. Patients enrolled under

protocol Version 3 or earlier will be summarized at the following visits: Days 1, 14 and 28. Patients enrolled under Version 4 or later will be summarized at the following visits: Screening, Days 14 & 28. Data will be combined for overlapping visits.

Eye Tracking and EEG

Eye tracking will not be included in the final study database. However, EEG data will be included in the final study database.

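### The SAP never summarises the CSHQ total score or its change from baseline, and CGI-S score change is described only indirectly through CGI-I

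*SAP*

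**What the plan says.** **CSHQ.** The protocol Synopsis lists as an exploratory endpoint "Change from baseline in the CSHQ scores". Protocol 6.7.2 asks for listings and descriptive statistics by treatment group for this endpoint, with means and change from baseline among them. SAP 6.1 gives the variable as "CSHQ total score". SAP 6.2 plans this: "The number and proportions will be summarized for each value in the assessment by visit, question, treatment and overall". It then names Day 1 as baseline. Table 45 is the only CSHQ table. Its shell has five response rows per question, and it is run in the Exploratory population.

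The Synopsis (Statistical Methods, safety and tolerability) also counts CSHQ among the tolerability measures: "specific laboratory abnormalities and change from baseline in the CSHQ scores in all treated patients".

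**CGI.** The protocol endpoint is "Change from baseline in the CGI-S scale, reflected by the CGI-I scale", and SAP 6.1 words it in nearly the same way. SAP 6.2 plans this: "Frequency counts and proportions for each response to the CGI-S and CGI-I assessments will be summarized by treatment and visit". It summarises patients enrolled under Version 3 or earlier at Days 1, 14 and 28, and those under Version 4 or later at Screening and Days 14 and 28. Only visits common to both are combined. Tables 47 and 48 are the resulting frequency tables for CGI-S and CGI-I.

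**The concern.** For CSHQ, the variable named in SAP 6.1 and the analysis in SAP 6.2 do not match. Followed as written, the plan produces no total score, no mean and no change, so its own endpoint is never summarised. The Day 1 baseline is named and then not used. This looks like an omission, because the same section gives raw and change-from-baseline statistics for ABC-C, SRS-2, the cognitive tests and lactate/pyruvate.

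For CGI-S, no change score or shift table is planned and no baseline is designated. The baseline ratings sit in two different visit rows.

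Protocol 3.2 says that exploring clinical improvement may help identify the endpoints most sensitive to change for a Phase 2 trial. A scale reported only as frequencies by visit cannot readily be compared on that footing with scales that get change scores.

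**Working it through.** The documents give no figure for this point. Their one sample-size calculation reproduces: 16 completers / (1 − 0.20) = 20 randomised. Nothing below depends on it.

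**Step 1. Trace each endpoint through the documents.**

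| | CSHQ | CGI-S |
|---|---|---|
| Protocol endpoint (Synopsis, 6.7.2) | change from baseline in scores | change from baseline, reflected by CGI-I |
| SAP 6.1 variable | total score | change from baseline, as reflected by CGI-I |
| SAP 6.2 baseline | Day 1 | none designated |
| SAP 6.2 analysis | item-response counts by visit | response counts by visit, for both scales |
| Tables | 45 | 47 (CGI-S), 48 (CGI-I) |
| Score change tabulated? | no | no; CGI-I ratings only |

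**Step 2. What Table 45 would contain.** Its five categories, never to always, match the 22-item abbreviated form in Protocol 4.6.1.8. That form at four visits (Screening, Day 1, Day 14, Day 28) and four columns (two doses, pooled placebo, overall) gives 22 × 5 × 4 × 4 = 1,760 cells. None of them is a total score or a change.

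**Step 3. Can a reader recover the endpoint from item counts?** With a scoring rule and complete data, the mean total equals the sum of the item means, so the mean change could be worked out by hand. The SD, median and range of the total could not, because they depend on how items combine within a patient. SAP 6.2 gives no scoring rule, so even the mean is not recoverable from the plan as written.

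**Step 4. Can a reader recover CGI-S change from Table 47?** Take invented ratings for six patients, with the same frequencies at both visits: 3, 4, 4, 5, 5, 6.

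- If each patient keeps the same rating, the changes are 0, 0, 0, 0, 0, 0: mean 0, SD 0, range 0 to 0.
- If the Day 14 ratings are 6, 5, 5, 4, 4, 3 in the same patient order, the changes are 3, 1, 1, −1, −1, −3. The mean is 0, the sum of squares is 22, the SD is √(22/5) = 2.10, and the range is −3 to +3.

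Table 47 is identical in both cases. With complete pairs, frequencies by visit fix the mean change but not its distribution.

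**Step 5. The split CGI-S baseline.** SAP 5.1 says that the first 4 patients followed the PK schedule in force before Version 4. Version 4 is also where the baseline CGI-S rating moves from Day 1 to Screening. If those 4 are the only earlier-version patients and all 16 planned completers enter the Exploratory population, the Day 1 row holds 4/16 = 25% of ratings and the Screening row 12/16 = 75%. Table 47 uses the whole treatment group as denominator, so neither row describes the group at baseline.

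**The case against.** The strongest objection concerns CGI. Both documents define the endpoint as CGI-S change reflected by CGI-I. CGI-I rates each patient directly against the pre-treatment state, with 4 meaning no change (Protocol 4.6.1.8), and Table 48 tabulates it by treatment and visit. A categorical description of change is therefore planned. This stands: a reader might infer that neither endpoint is described at all, and for CGI that is not so. What is missing is the CGI-S score change. Each protocol version also schedules one baseline CGI-S rating (SAP 1.2), so the split is a matter of definition and no data are lost.

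A reader might also infer that sleep data vanish for patients who stop early. They do not. Such patients are asked back on Day 28, when CSHQ is scheduled, and Data Listing 28 covers the Safety population. They can be left out of the summary table, but not out of the listing. The body of that listing's shell is not legible in the text available, so a total-score column there cannot be excluded. Even so, a listing does not replace the summary in Protocol 6.7.2.

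The Synopsis wording, "change from baseline in the CSHQ scores in all treated patients", is a single sentence. The exploratory objectives, the outcome measures and Protocol 6.7.2 all class CSHQ as exploratory, and it is absent from the protocol's lists of safety endpoints and from SAP 4.1. That sentence does not by itself require the analysis to move to the Safety population. It is an inconsistency to resolve.

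The form in use is also less open than the protocol text suggests. "Items are rated on a three-point scale" describes the 45-item questionnaire, while the Table 45 categories fit the abbreviated one. What remains missing is the scoring rule.

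Finally, the endpoints are descriptive, in a study not designed to test efficacy. That limits the consequence but does not remove the mismatch.

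**Conclusion.** The point holds in full for CSHQ: SAP 6.2 and Table 45 never summarise the total score that SAP 6.1 names, or the change that the protocol sets as endpoint. For CGI it holds in a narrower form: CGI-S score change is not summarised, its baseline is not defined, and change is visible only through CGI-I frequencies.

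The size is modest. Two exploratory endpoints are affected, with up to 6 completers per active dose and up to 4 on pooled placebo. No primary conclusion changes. Two numerical readings that a reader might reach are not supported. Table columns would not be planned at 2 patients, because placebo is pooled across cohorts. And the 20% dropout is a planning assumption that does not measure how many patients Table 45 would omit, since Exploratory exclusions also cover major protocol violations.

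The conclusion assumes that Table 45 is the complete planned CSHQ summary and that its five categories identify the abbreviated form. For CGI-S it also assumes that the Day 1 rating under earlier versions was made before the first dose, which SAP 1.2 does not state.

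**What to change.** 1. In SAP 6.2, state which CSHQ form was used and its scoring rule, including any reversed items. Add a table of the raw total score and its change from Day 1 at Days 14 and 28, by treatment. The Day 1 baseline can stay: SAP 1.2 lists CSHQ at Day 1 without restriction by protocol version, whereas Screening CSHQ exists only from Version 4. Subscale scores need not be added unless a key for the form in use is supplied.
2. Either present that table for the Safety population as well, or reconcile the Synopsis sentence on tolerability with the SAP's choice of the Exploratory population.
3. Define the CGI-S baseline as the single pre-dose rating (Day 1 under Version 3 or earlier, Screening under Version 4 or later), show it as one baseline row, and add a CGI-S change or shift table. Keep Table 48.

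The cost is two extra descriptive tables and a few lines of SAP text. All the data are already collected under the schedule.
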